1.0 Research Design

1.1 Purpose/Specific Aims

The purpose of this study is to evaluate the efficacy of Nitazoxanide (NTZ), Ribavirin (RBV) and Hydroxychloroquine (HCQ) versus placebo in participants with proven SARS-CoV-2 infection who are asymptomatic or mildly symptomatic with COVID-19. Those with illness requiring hospitalization, or who present with hypoxia (PO2<92%) or shortness of breath at time of enrollment are excluded.

A. Objectives

In participants with proven SARS-CoV-2 infection who are asymptomatic or mildly symptomatic with COVID-19 randomly allocated to nitazoxanide, ribavirin plus hydroxychloroquine (NTZ, RBV + HCQ) or placebo.

Primary Objective:

To assess the rate of decline in viral load over the 10 days after randomization between participants treated with NTZ, RBV + HCQ for COVID-19 and placebo.

Secondary Objective:

- 1. To compare the proportion of participants with virus below LLOQ at day 10
- 2. To compare the proportion of participants who are asymptomatic and symptomatic at day 10
- 3. To compare the time of onset and frequency of the development of fever and other symptoms of COVID-19 in those who were asymptomatic at enrollment
- 4. To compare the progression in severity of COVID-19 symptoms (hospitalization and length of stay; admission to intensive care unit and number of days in unit; intubation, Death (any cause))
- 5. To compare the severity of disease in participants who develop symptoms of COVID-19
- 6. To compare the side effects of NTZ, RBV + HCQ compared to placebo
- 7. To determine whether baseline viral load predicts response to therapy
- 8. To assess the rate of decline in viral load over days 3 and 6 after randomization
- 9. To assess new, self-reported COVID-19 infection in household members

B. Hypotheses / Research Question(s)

We hypothesize that treatment with NTZ, RBV + HCQ decreases viral load and the progression of symptoms, or emergence of symptoms in those who are asymptomatic at baseline, in SARS-CoV-2-positive adults compared to placebo.

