 Adverse Events Based on Signs and Symptoms When collecting AEs, the recording of diagnoses is preferred (when possible) to recording a list of signs and symptoms. However, if a diagnosis is known and there are other signs or symptoms that are not generally part of the diagnosis, the diagnosis and each sign or symptom will be recorded separately.

D. Data Points

Case Report Forms

Completion of the electronic case report forms (eCRFs) will be done in accordance with the instructions outlined in the study specific data capture plan. All eCRFs are considered the primary

data collection document for the study and are stored in REDCap in a confidential format. Only key personnel who are delegated in the delegation of authority log are permitted to make entries, changes, or corrections in the eCRF. All users will complete user training, as required or appropriate per regulations. An audit trail will be maintained automatically by the electronic CRF management system.

Data Points to be collected:

- Baseline medical history
- Treatment compliance
- Daily temperatures
- Symptoms of disease
- Adverse events
- Concomitant medications
- Any standard of care treatments or procedures to manage COVID-19
- Viral load from saliva specimen
- Viral load from mid-turbinate self-nasal swab
- SARS-CoV-2 infections confirmed or suspected in household members

Data Submission Timeline and Forms

Completion of eCRFs will occur within 72 hours of study time point unless otherwise indicated. Baseline (pre-study) eCRFs (e.g., enrollment, medical history, concomitant medications, etc.) will be completed no later than 24 hours after the start of treatment.

E. Study Duration

Study participants will be treated for five (5) days and will then remain on follow-up for up to 28 days after entry into the study. The estimated time to complete the entire study including data analysis is 3-6 months

F. Endpoints

Primary endpoint:

1. Rate of decline in viral load over the 10 days after randomization

Secondary:

- 1. Proportion of participants with virus below LLOQ at day 10
- 2. Proportion of participants asymptomatic at day 10.
- For those who were asymptomatic at baseline: Progression to symptoms--presence or absence of key symptoms: fever ≥ 100.4^o F (38 ^o C); sore throat, cough, shortness of breath, myalgias, vomiting or diarrhea, or change in smell or taste

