6.0 Data Management Plan

6.1 Data Analysis

We will follow intention-to-treat principles and analyze the groups as randomized. A summary table of baseline variables will be created with means and standard deviations for continuous variables or percentages for categorical variables, all stratified by treatment group.

Primary outcome. We will have repeated measures of log10 VL for each participant. These measurements will occur on day 0 (baseline) and at about days 3, 6 and 10. We will fit a linear mixed effects model, where log10 VL is the outcome, indicators for treatment group (SoC reference), time, and treatment by time interactions are the predictors. The model will include a random slope and intercept, to account for within participant correlation. The robust sandwich variance will be used to estimate standard errors. Because we are estimating within participant changes over time from randomization, we can estimate a treatment effect at any particular day. Our primary hypotheses involve the change over time, which we will assess with the treatment by time interaction terms. If participants drop out from the study

before the day 10 visit, we will use all of their preceding data. Linear mixed effects models rely on the assumption that missing data are missing at random.

Secondary outcomes. For binary outcomes, such as progression to having symptoms, intubation, death, hospitalization, and admission to intensive care unit, we will fit logistic regression models. The covariates will include the treatment group indicators. We will report odds ratios and 95% confidence intervals. For change variables, such as change in viral shedding or change in Q-T interval, we will fit linear mixed effects models (similar to primary outcome).

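### Secondary Objective 3 compares time of symptom onset as well as frequency, but its endpoint is yes/no with no assessment day and its logistic regression answers only the frequency half

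*Combined protocol and SAP*

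**What the plan says.** Section 1.1, Secondary Objective 3, reads: "To compare the time of onset and frequency of the development of fever and other symptoms of COVID-19", restricted to participants without symptoms at enrollment. It asks for two comparisons, one of timing and one of frequency.

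Section 1.3 F, secondary endpoint 3, defines the outcome for those asymptomatic at baseline as "Progression to symptoms--presence or absence of key symptoms", followed by a symptom list. It gives no onset time and no day of assessment.

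Section 6.1, under secondary outcomes, says: "For binary outcomes, such as progression to having symptoms, intubation, death, hospitalization, and admission to intensive care unit, we will fit logistic regression models". On the model content it adds "The covariates will include the treatment group indicators", and on reporting "We will report odds ratios and 95% confidence intervals". The only other secondary method is for change scores: "For change variables, such as change in viral shedding or change in Q-T interval, we will fit linear mixed effects models". Neither document part contains a time-to-event method.

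Section 1.9 provides for symptom questionnaires every day for 10 days and again on day 28. Section 1.3 stratifies randomization by symptom status with separate tables, so the asymptomatic stratum is a randomized comparison in its own right.

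**The concern.** The objective, endpoint and analysis do not line up. The onset day will be known to within a day through day 10, yet the plan followed as written never uses it. This is more than a missing detail, because a method is named for the outcome and that method carries no information about when symptoms began.

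At stake is half of one secondary objective. If treatment postponed symptoms without changing who eventually had them, the planned odds ratio would show nothing. Any onset-time comparison added after unblinding would be post hoc. The missing assessment day adds a second ambiguity: the same data can give different odds ratios at day 10 and at day 28.

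**Working it through.** The documents give no power, incidence or effect size for this objective, so there is no stated figure to reproduce. The check has three steps.

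**1. Inputs.** From the documents: 35 per arm (section 1.5), daily symptom records to day 10 and one at day 28 (section 1.9), and a treatment-only logistic model (section 6.1). The 95% intervals imply a two-sided 5% level; no alpha is stated. Assumed, because the documents are silent: 12, 17 or 35 asymptomatic participants per arm (35 is the upper limit, 17 about half), final symptom incidence of 50% or 80%, placebo onset spread evenly over days 1–6, and a treatment effect that only shifts onset.

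**2. What a shift does to the odds ratio at day 10.** Take 80% incidence.
- 4-day delay: onsets fall on days 5–10, all inside the window. Incidence is 80% in both arms, so the odds ratio is 1.
- 6-day delay: onsets fall on days 7–12, with 4 of 6 inside the window. Treated incidence is 0.80 × 4/6 = 53%, so the odds ratio is (0.533/0.467)/(0.80/0.20) = 1.14/4 = 0.29.
- 8-day delay: onsets fall on days 9–14, with 2 of 6 inside. Treated incidence is 0.80 × 2/6 = 27%.

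With a day-28 cutoff, all three delays return to an odds ratio of 1.

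**3. Rejection rates.** The binary test is the score test z = (p₁ − p₂)/√[p̄(1 − p̄)(2/n)], which tests the treatment term in a treatment-only logistic model. The log-rank test uses onset day, censored at day 10. There are 2,000 simulated trials per row and no dropout.

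| n per arm | Incidence | Delay (days) | Binary | Log-rank |
|---|---|---|---|---|
| 12 | 50% | 2 | 6% | 6% |
| 12 | 50% | 4 | 7% | 11% |
| 12 | 80% | 2 | 4% | 20% |
| 12 | 80% | 4 | 3% | 43% |
| 17 | 50% | 2 | 6% | 8% |
| 17 | 50% | 4 | 6% | 12% |
| 17 | 80% | 2 | 6% | 26% |
| 17 | 80% | 4 | 5% | 51% |
| 35 | 50% | 2 | 5% | 10% |
| 35 | 50% | 4 | 4% | 17% |
| 35 | 80% | 2 | 6% | 40% |
| 35 | 80% | 4 | 5% | 77% |

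The binary test stays at 3–7%, around its nominal level. At 17 per arm and 80% incidence, the longer delays give binary power of 39% (6 days) and 92% (8 days) with a day-10 cutoff, and about 5% for both with a day-28 cutoff.

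**Sensitivity to the onset model** (17 per arm, 4-day delay). At 70–80% incidence the log-rank test rejects in about 34–53% of trials under evenly spread onset. Under exponential onset with 10% dropout it rejects in 13–35%, depending on how the delay is modelled. At 30–50% incidence the figure is about 6–12%. If the effect is instead a constant hazard ratio of 0.4, the two tests perform alike: 47–51% binary against 48–55% log-rank.

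**The case against.** Several stronger readings are tempting, and the documents do not support them.

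- *That no delay could be detected.* This is true only when incidence at the cutoff is equal in the two arms. Step 2 shows that a 6- or 8-day delay lowers day-10 incidence and can be picked up, though it would be read as a difference in frequency. Whether that happens depends on a cutoff that endpoint 3 leaves open.
- *That the logistic model fails the objective.* It answers the frequency half properly. The hypothesis in section 1.1 B speaks of reducing the emergence of symptoms, which reads naturally as frequency.
- *That everyone who stops answering must be dropped or miscounted.* A participant whose onset was recorded before stopping is a known event. Only those who stop while symptom-free are unresolved, and the day-28 questionnaire and the record review in section 1.9 B may settle some of them.
- *That a large amount of power is being lost.* The gain is sizeable only with high incidence and a pure delay. A qualifying test may be up to 7 days old, so people still symptom-free at entry might convert less often; the documents give no rate. No passage predicts a pure delay.

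It is also fair to say that this is one half of one of nine secondary objectives, in a stratum of unstated size, and that the onset dates will be collected in any case. These points limit the importance of the matter. They do not remove the mismatch: an objective that names onset time has no endpoint or analysis for it.

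**Conclusion.** The point stands in limited form. Secondary Objective 3 promises a comparison of onset time that the endpoint and section 6.1 do not deliver, and endpoint 3 lacks an assessment day. A delay that leaves cumulative incidence at the cutoff unchanged would be rejected at about 4–6%, which is chance; a longer delay would surface only as a frequency effect.

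A time-to-event analysis would answer the question as asked, but with limited power. The power figures rest on assumed stratum size, incidence, delay and onset pattern, and they show a range rather than forecast this trial. The analysis should be added, at the weight of a secondary-endpoint correction. Nothing here touches the primary viral-load comparison.

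**What to change.** In section 1.3 F, add an endpoint for participants asymptomatic at baseline: days from randomization to the first key symptom, taken from the daily questionnaires on days 1–10. Censor at the last completed daily questionnaire, and at day 10 at the latest.

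In section 6.1, specify Kaplan-Meier curves by arm, a log-rank test and a Cox hazard ratio with its 95% interval. Because a pure delay is not a constant hazard ratio, the curves should carry the interpretation. Keep the logistic model for the proportion with symptoms by day 10, state that cutoff in endpoint 3, and say how participants who stop reporting while symptom-free are counted.

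The cost is plan wording and one further secondary analysis on data already being collected. It brings an assumption that censoring is non-informative, which could fail if people stop answering because they fall ill, and power will be limited. If the sponsor does not want the comparison, removing time of onset from Objective 3 would also restore consistency, at the price of giving up that question.

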1.2 Research Significance

From its origins in late 2019 at a wet seafood market in Wuhan, China, infection with severe acute respiratory syndrome coronavirus-2 (SARS-CoV-2) has rapidly become a global pandemic ¹. The clinical manifestations of coronavirus disease-2019 (COVID-19) range from asymptomatic carriage and mild upper respiratory symptoms to severe pneumonia, respiratory failure, sepsis, and death ². Viral transmission appears to occur predominantly via inhalation or by contact with infectious droplets ³. In addition to spread from symptomatic persons, pre-symptomatic and asymptomatic hosts also can transmit SARS-CoV-2, complicating efforts to contain its spread ⁴.

Since the virus is novel in humans and pre-existing immunity appears to be lacking, estimates of its spread are guided by previous pandemics of new influenza strains that could infect 50-70% of the world population within 2 years ⁵. SARS-CoV-2 is highly infectious, with estimated R₀ between 2 and 4, and doubling in many countries about every 4 days ⁶. The U.S has experienced similar exponential spread, and despite community efforts to encourage social distancing through school and event cancellations, remote workplaces, and self-quarantining, many experts predict that the U.S. health care system, like those in parts

of Europe and Asia, will soon be overwhelmed with new cases, with hospitals and healthcare workers (HCW) facing unprecedented challenges ^{7, 8}

A triple combination antiviral coronavirus therapy (TriACT) comprised of hydroxychloroquine sulfate, ribavirin, and nitazoxanide for the treatment of acute illness due to SARS-CoV-2 infection is being tested in the study. Each of these drugs is currently available as oral drug product approved for marketing in many of the major world markets. In the US, they are available under the trade names, PLAQUENIL[®] (hydroxychloroquine sulfate, USP) tablets, for oral use; Rebetol[®] (ribavirin, USP) capsules and oral solution, for oral use; or Alinia[®] (nitazoxanide) tablets, for oral use.

The pharmacological rationale for the treatment of SARS-CoV-2 with a triple combination antiviral therapy is based on two distinct rationales: i) high antiviral potency through synergy, in order to block viral replication, and ii) creating a high genetich barrier to antiviral drug resistance. It was previously discovered that by carefully selecting drugs that block sequential steps in viral replication could lead to synergy, or a multiplicative increase in antiviral potency. The triple combination therapy of amantadine, ribavirin and oseltamivir was shown to be 20-fold synergistic, in both in vitro models and in vivo models.⁹ This product was evaluated in a global Phase 2 clinical trial conducted by NIH/NIAID, which showed that this three- antiviral drug combination significantly reduced viral load compared to oseltamivir alone.¹⁰ The in vitro pharmacology of hydroxychloroquine sulfate, ribavirin, and nitazoxanide has been examined in SARS-CoV-2 and related viral infections, and have all demonstrated promising, yet modest effects, on slowing viral replication in vitro and in vivo. These drugs sequentially block steps in the SARS-CoV-2 viral replication life cycle, including uncoating, replication and reassembly of virus particles in the host human cells. Each of these drugs exhibit effective antiviral concentrations (or EC50s) ~1 µg/ml based upon in vitro data in corona virus infected cell lines that approximate the blood concentration ranges of their respective labels:

٠	Hydroxychloroquine:	0.24 to 2.4 µg/ml ^{11,12}
٠	Ribavirin:	4 to 8 µg/ml ¹³
٠	Nitazoxanide:	0.3 to 1 µg/ml ¹⁴

In addition to the direct antiviral activity of the triple combination each of the individual drugs has documented immunomodulatory activities that may contribute to the overall impact on the host.¹⁵⁻¹⁷ Combining drugs with both direct antiviral and immunomodulating activity is a rational approach based on the pathophysiology of the infection where immune dysregulation and hyperinflammatory responses contribute to multi-organ dysfunction and death(cytokine storm).

The clinical efficacy, safety, and pharmacokinetics of orally administered hydroxychloroquine sulfate, ribavirin, and nitazoxanide have been investigated as monotherapies in SARS-CoV-2 and related infections.

Hydroxychloroquine has been widely studied in clinical trials for coronaviruses, including COVID19. In a randomized controlled trial (RCT) comparing HCQ (n = 31) versus no HCQ (n = 31) in mild to common COVID-19 (NHC criteria) patients, Chen et al. reported that the HCQ group had shorter time to clinical recovery and radiologic improvement in pneumonia.¹⁸ A non-randomized case-control study in France, which compared HCQ (n = 14) and HCQ plus azithromycin for prevention of bacterial superinfection (n = 6) against a control group (n = 16). At day 6 of treatment, all patients in the HCQ plus azithromycin group tested virus-free, compared to 57.1% in the HCQ-alone group and 12.5% of the control group (P <0.001).¹⁹ Other studies have shown less favorable results. A small non-blinded RCT in China comparing HCQ (n = 15) against a control group (n = 15) in patients with common COVID-19 (NHC criteria) showed that following 7 days of treatment, throat swabs were negative for the virus in 86.7% of the HCQ group compared to 93.3% of the control group (P > 0.05).²⁰ The mean duration from hospitalization to viral clearance was comparable in both groups. Results of combination therapy from a retrospective cohort study of 368 males from the US Veterans Health Administration medical centers who received either

HCQ, HCQ plus azithromycin or no HCQ for COVID-19 of varying severities showed that the risk of death from any cause was higher in the HCQ group (adjusted hazard ratio (HR) = 2.61; 95% CI: 1.10–6.17; P = 0.03) compared to the no-HCQ group.²¹ The risk of ventilation was no different in patients who did not receive HCQ compared to those who received HCQ alone (adjusted HR, 1.43; 95% CI: 0.53–3.79; P = 0.48) or with azithromycin (adjusted HR = 0.43; 95% CI: 0.16–1.12; P = 0.09). The risk of death after ventilation also was not significantly different across the 3 groups.

The safety of HCQ in Covid patients has been examined in multiple studies of varying rigor. HCQ use, with or without azithromycin among patients hospitalized with COVID-19 in retrospective cohort study of 1438 patients hospitalized in metropolitan New York, treatment with HCQ, azithromycin, or both was not associated with significantly lower in-hospital mortality.²² In another study in New York City, Investigators analyzed 1,376 COVID-19 patients who had been admitted to the hospital , including 811 who received a 5-day course of HCQ.²³ The time-to-event analysis found no greater—or lower—risk of intubation or death with hydroxychloroquine recipients vs. nonrecipients. Three studies have investigated the use of HCQ in severe COVID-19 patients that have reported prolongation of QT intervals. In a prospective case series of 11 severe COVID-19 patients treated with HCQ plus azithromycin, 1 patient discontinued treatment due to prolonged QT interval.²⁴ In a cohort study of 181 patients with severe COVID-19 within 48 hours of admission, 8 (9.5%) of 84 patients in the HCQ group discontinued HCQ after 4 days due to prolonged QT interval or first-degree atrioventicular block.²⁵ Perinel et al. examined HCQ dosing in severe to critically ill COVID-19 patients by studying the pharmacokinetic properties of HCQ in 13 COVID-19 ICU patients. In the study, HCQ was withdrawn in 2 (15.4%) patients due to prolonged QT intervals.²⁶

Spontaneous reports to pharmacovigilance centers and drug manufacturers provide an additional important source of information that can be used to detect rare adverse events. A summary from the WHO Global Database of Individual Case Safety Reports listed a total of 40 cases of sudden death and/or death as an outcome of TdP/QT interval prolongation following any antimalarial treatment, all of which originated in Europe and North America.²⁷ In 22 cases, the antimalarial was used for an indication other than malaria, with drug dosages and durations varying accordingly. In 16 cases, concomitant use of another medicine that could potentially increase the risk of QT/QTc interval prolongation was reported. Quinidine was the suspected antimalarial in 16 cases; in 12 of these cases, there was evidence of a cardiac-related indication and/or concomitant medications, suggesting quinidine was used as an antiarrhythmic. Exposure to chloroquine and hydroxychloroquine was reported in six and five cases of sudden death, respectively. In four of these cases, overdose was listed as the indication. Hydroxychloroquine was used to treat rheumatoid arthritis, systemic lupus erythematosus and small cell lung carcinoma in one case each.

The clinical efficacy of ribavirin has been reported in small research studies on the treatment of coronaviruses during the SARS-CoV outbreaks in China and North America, and MERS-CoV outbreaks in the Middle East and Asia. No clinical study has documented a therapeutic benefit of ribavirin monotherapy for treatment of corona virus infections. Results from a retrospective cohort study of the combination of oral ribavirin with interferon alpha significantly improved survival and in the first reported case of MERS-COV in south Korea lead to successful recovery after early treatment.^{28,29} In a published case report, triple therapy with Lopinavir/ritonavir, interferon alpha and oral ribavirin in a patient with MERS-CoV infection led to virologic clearance after 6 days of treatment and a full recovery at day 13.³⁰ In a prospective, open-label, randomized, phase 2 trial in adults with COVID-19 who were admitted to six hospitals in Hong Kong, patients were randomly assigned to a 14-day combination of lopinavir 400 mg and ritonavir 100 mg every 12 h, ribavirin 400 mg every 12 h, and three doses of 8 million international units of interferon beta-1b on alternate days (combination group) or to 14 days of lopinavir 400 mg and ritonavir 100 mg every 12 h (control group).³¹ Results showed that triple antiviral therapy was safe and superior to lopinavir-ritonavir alone in alleviating symptoms and shortening the duration of viral shedding and hospital stay in patients with mild to moderate COVID-19. Finally, a large phase 2 study was conducted in influenza patients examining triple combination antiviral drug (TCAD) regimen composed of ribavirin, amantadine, and oseltamivir versus oseltamivir monotherapy with matching placebo. A

significant decrease in viral shedding was observed at day 3 relative to monotherapy, however the difference was not associated with improved clinical benefit.¹⁰

Hemolytic anemia is a common dose-dependent side effect that frequently complicates prolonged use of ribavirin for treatment of HCV. Two studies have confirmed similar decreases in hemoglobin level that were linearly related to steady-state plasma concentrations of ribavirin and that hemoglobin levels of <8.5 g/dL occurred when the steady-state ribavirin concentration increased above 3.5 mg/mL.^{32,33} However, in short courses of treatment for influenza and COVID-19 mentioned above, no significant decrease was reported.^{10,31}

Nitazoxanide, in addition to antiparasitic activity, has broad-spectrum in vitro antiviral activity against influenza, RSV, norovirus, rotavirus, and hepatitis B and C viruses and has shown In vitro activity against MERS-CoV and other corona viruses.¹⁴ Clinical results for treatment of viral infections have been mixed. In one phase 2b/3 clinical trial, oral administration of nitazoxanide 600 mg twice daily for five days reduced the duration of clinical symptoms and reduced viral shedding compared to placebo in patients with influenza.³⁴ However, in a phase 2 study of nitazoxanide + SOC in patients with severe acute respiratory illness (SARI), nitazoxanide did not reduce the duration of hospital stay, supplemental oxygen use, or shedding of respiratory viruses on day 3 in patients with SARI.³⁵

Nitazoxanide is generally well tolerated. In the study by Haffizulla et al., adverse events were similar between groups, the most common being headache reported by 24 (11%) of 212 patients enrolled in placebo group, 12 (6%) of 201 patients in the nitazoxanide low-dose group, and 17 (8%) of 211 patients in the nitazoxanide high-dose group, or diarrhea, reported by seven (3%) patients in the placebo group, four (2%) patients enrolled in the nitazoxanide low-dose group, and 17 (8%) patients in the nitazoxanide high-dose group.³⁴ Similar safety and tolerability was seen in the study by Gamiño-Arroyo et al which reported the similar frequency of adverse events between nitazoxanide and placebo, the most common being gastrointestinal disorders (31.9%), infections and infestations (16.3%) and respiratory and thoracic disorders (16.3%).³⁵

The pharmacokinetics of hydroxychloroquine, ribavirin, and nitazoxanide are summarized below.

Following a 200 mg oral dose, hydroxychloroquine reached a Cmax of 129.6ng/mL with a Tmax of 3.26h in the blood and a Cmax of 50.3ng/mL with a Tmax of 3.74h in the plasma. Oral hydroxychloroquine has an absorption half-life of 3-4 hours. A 200 mg oral dose of hydroxychloroquine has a half-life of 537 hours or 22.4 days in blood, and 2963 hours or 123.5 days in plasma. Steady state modelling of steady state dosing of HCQ has been carried out, showing that a 400 mg BID loading dose, followed by 200 mg BID for 5 days results in the unbound Css of 600 ng/ml, with lung concentrations >10,000 ng/ml¹¹(Smith et al 2020, data on file). Based on a clinical study, hydroxychloroquine is a weak-to-moderate inhibitor of CYP2D6 (causing about a 65% increase in exposure of metoprolol).

After oral ingestion of ribavirin, the plasma concentration exhibits a characteristic three-phase profile, consisting of two rapid phases (absorption and distribution) and one long terminal elimination phase. Ribavirin is promptly absorbed into circulation, with the help of gastrointestinal, sodium-dependent nucleoside transporters in the proximal small bowel. The average time to reach Cmax is 2 hours after oral administration of 1200 mg ribavirin. Following administration of 1200 mg/day with food for 12 weeks mean±SD (n=39; body weight greater than 75 kg) AUC was 25,361±7110 ng·hr/mL and C was 2748±818 ng/mL. The terminal half-life of ribavirin following administration of a single oral dose of ribavirin is about 120 to 170 hours. The total apparent clearance following administration of a single oral dose of ribavirin is about 26 L/h. After 5 days of dosing, Ribavirin levels approaching 3000 ng/ml are achieved with 600 mg BID dosing (Wu, et al, 2018). Ribavirin is eliminated by metabolism and renal elimination, with the latter accounting for about 5–15% of single dose elimination.

The active metabolite of NTZ is tizoxanide (desacetyl-nitazoxanide). The initial reaction in the metabolic pathway of Nitazoxanide is hydrolysis to tizoxanide, followed by conjugation, primarily by glucuronidation to tizoxanide glucuronide. Following a 500mg oral dose, tizaxoadnide reached a Cmax of 10600 ng/mL with a Tmax of 3 h in the plasma. When administered with food, the AUC of tizoxanide and tizoxanide glucuronide in plasma is increased to almost two-fold and the maximum concentration is increased by almost 50% compared to when ingested without food. Following oral administration of a single nitazoxanide tablet every 12 hours for 7 consecutive days, there was no significant accumulation of nitazoxanide metabolites tizoxanide or tizoxanide glucuronide detected in plasma.

In summary, there do not appear to be overlapping or synergistic toxicities among the drugs. It is not expected that co-administration of these drugs will result in increased safety concerns compared to the drugs given individually. Pharmacokinetic interactions are also not expected to occur, given that each is cleared via differing mechanisms. The use of TriACT has not been investigated in clinical studies to date.

